ATTACHMENT C. INFORMED CONSENT FORM

ATTACHMENT D. LATERA INSTRUCTIONS FOR USE

ATTACHMENT E. FINANCIAL DISCLOSURE FORM

ATTACHMENT F. CASE REPORT FORMS AND PATIENT REPORTED OUTCOMES

ATTACHMENT G. PATIENT AND SITE BROCHURE

# **Revision History**

Version Version Number Date		Affected Section(s)	Summary of Revisions Made:
1.0 12-FEB- OI 2018 OI		Original	Initial Release

Date

# STATISTICAL ANALYSIS PLAN

### **1 ABBREVIATIONS AND ACRONYMS**

Acronym	Description		
AE	Adverse Event		
BMI	Body Mass Index		
CI	Confidence Interval		
СРАР	Continuous Positive Airway Pressure		
DMC	Data Monitoring Committee		
ESS	Epworth Sleepiness Scale		
FESS	Functional Endoscopic Sinus Surgery		
ICF	Informed Consent Form		
IRB	Investigational Review Board		
ITT	Intention-to-Treat		
LWI	Lateral Wall Insufficiency		
MedDRA	Medical Dictionary for Regulatory Activities		
mITT	Modified Intention-to-Treat		
NAO	Nasal Airway Obstruction		
NOSE	Nasal Obstruction Symptom Evaluation scale		
NVC	Nasal Valve Collapse		
OSA	Obstructive Sleep Apnea		
РР	Per Protocol		
PRO	Patient-reported Outcomes		
SAE	Serious Adverse Event		
SAP	Statistical Analysis Plan		
SD	Standard Deviation		

ST 800-A

# STATISTICAL ANALYSIS PLAN

VAS	Visual Analogue Scale
-----	-----------------------

ST 800-A

### STATISTICAL ANALYSIS PLAN

#### **2 INTRODUCTION**

Nasal airway obstruction (NAO) can be caused by several independent or concomitant factors including septal deviation, enlarged turbinates or a weakened nasal lateral wall, leading to nasal valve collapse (NVC). Surgery to strengthen the lateral wall has been shown to significantly improve the quality of life for subjects suffering from NAO, however current procedures are generally invasive and have the potential to permanently alter the patient's appearance. This study utilizes a minimally invasive technique to address NVC by supporting the nasal lateral wall cartilage with an absorbable implant. Spirox has developed the Latera Absorbable Nasal Implant and Delivery Device, to enable a less invasive alternative to current surgical approaches used to support weak lateral wall cartilage.

The study purpose is to evaluate the Latera Absorbable Nasal Implant (Latera Implant) versus Sham Control in subjects with nasal valve collapse due to or primarily due to insufficient cartilaginous support of the lateral nasal wall.

#### 2.1 Design, Treatments and Visits

This clinical study is to evaluate the performance of the device in comparison to no intervention, in this case, a "sham treatment". The study design and methods have been developed using input from previous and ongoing studies with the Latera Implant. This randomized, single-blind, sham-controlled, multicenter study of the Latera Nasal Absorbable Implant will enroll subjects with nasal valve collapse due to or primarily due to insufficient cartilaginous support of the lateral nasal wall into one of two treatment arms, a) implantation with the Latera device or b) Sham Control.

There are three treatment arms:

Latera Treatment Arm

Subjects in the active treatment arm will receive the Latera Implant, a PLLA-PDLA copolymer, delivered to the region of the lateral nasal wall cartilages to provide support. It is placed using standard, minimally invasive techniques and is absorbed over a period of approximately 18 months.

ST 800-A

### STATISTICAL ANALYSIS PLAN

Sham Control Arm

Subjects in the Sham Control arm will undergo the same preoperative assessments as those in the Latera Treatment arm up to and including anesthesia for the implant and cannula insertion into the nasal lateral wall, however, no implant will be placed.

Randomization to the Sham Control Arm will be assessed by the independent Data Monitoring Committee (DMC) at each interim analysis time point. If the pre-determined efficacy, safety, or operational criteria are met, randomization may be terminated.

#### **Crossover Subjects**

Subjects will be unblinded after the 3-month assessment is complete. For subjects in the Sham Control arm, the subject will be treated with the Latera Implant if they still meet all eligibility criteria. The subject's data will continue to be recorded thereafter through 24 months post-implant. If the subject does not meet the eligibility criteria, he/she will exit the study.

For subjects randomized to the Latera Implant arm, the follow-up evaluations will be at 7 days, 30 days, 3 months, 6 months, 12 months, 18 months, and 24 months post-procedure. For subjects randomized to the Sham Control arm, the follow-up evaluation will be at 7 days, 30 days, and 3 months.

#### 2.2 Objectives

The primary objective of the LATERA RCT is to demonstrate the superiority of the Latera Implant to improve nasal breathing, compared with a Sham Control procedure.

#### 2.3 Subject Population

There are up to 150 subjects who will be recruited from sites' existing patient populations that are seeking treatment for nasal airway obstruction including nasal valve collapse. Anatomical considerations may impact the race distribution (e.g. some races may be less prone to lateral wall collapse), but the intention is to enroll all eligible subjects.

Study brochures containing information on study participation and the Latera Implant may be provided to the sites, as well as posters that may be displayed either as hard copies or

# STATISTICAL ANALYSIS PLAN

electronically on computer monitors in the office. All recruiting materials must be approved by the appropriate Investigational Review Board (IRB) (central or local).

#### 2.3.1 Patient Eligibility

The trial will include up to 150 subjects at up to 15 investigational sites, male and female, aged 18 and above who are appropriate candidates for nasal intervention with the Latera Implant.

#### Inclusion Criteria

Subjects must meet the following criteria to be included in the study:

- 1. Adults aged 18 and above;
- 2. Understands and provides written informed consent;
- 3. Stated willingness to comply with all study procedures, post-treatment care and availability for the duration of the study follow up of 2 years;
- 4. In good general health as evidenced by medical history;
- 5. NOSE score  $\geq$ 55;
- 6. Dynamic bi-lateral nasal wall insufficiency as confirmed by Positive Modified Cottle Maneuver;
- 7. Nasal and facial anatomy appropriate to receive the Latera Implant;
- 8. Documented failure of benefit after at least 4 weeks of conservative medical management, including, for example, antihistamines or nasal steroids, evidenced by lack of efficacy or tolerability.

#### Exclusion Criteria

Subjects meeting any one of the following criteria are ineligible for study participation:

- 1. Unable to tolerate or not a candidate for procedures performed under local anesthesia;
- 2. Pathology other than lateral wall insufficiency (e.g. septal deviation, turbinate or adenoid hypertrophy, polyps, sinusitis, rhinitis) is the primary contributor to airway obstruction;
- 3. Requires or is anticipated to require any other concurrent nasal procedures (e.g. Functional Endoscopic Sinus Surgery (FESS), rhinoplasty, sinuplasty, septoplasty, or turbinate reduction) outside of the index procedure within 12 months after the index procedure;

ST 800-A

## STATISTICAL ANALYSIS PLAN

- 4. FESS, sinuplasty, septoplasty, inferior turbinate reduction, or rhinoplasty within the past 6 months;
- 5. Any other rhinoplasty procedures are planned or planned usage of external dilators within 24 months after the index procedure;
- 6. Permanent nasal implant of any type (e.g. autologous, homologous, or synthetic graft) or dilator;
- 7. Presence of concomitant inflammatory or infectious conditions or unhealed wounds in the treatment area (e.g., vestibulitis, vasculitis, active acne),
- 8. Currently use of chronic systemic steroids or recreational intra-nasal drugs;
- 9. Currently has cancerous or pre-cancerous nasal lesions, has had radiation in the treatment area, or is currently receiving chemotherapy;
- 10. History of a significant healing disorders including hypertrophic scarring, or keloid formation;
- 11. Poorly controlled diabetes mellitus;
- 12. Known or suspected allergy to PLA or other absorbable implant materials in the Latera Implant;
- 13. Severe obstructive sleep apnea (OSA) and cannot or is unwilling to refrain from continuous positive airway pressure (CPAP) for 4 weeks post-procedure, in agreement with the treating physician;
- 14. Female subjects, of child bearing potential, known or suspected to be pregnant or are lactating;
- 15. Any other presenting condition that, in the medical opinion of the investigator, would disqualify the subject from the study.

#### 2.4 Sample Size Considerations

The primary analysis will be based on a 1-sided binomial test of proportions. Assuming a Sham Control response rate of 40% and a Latera Treatment response rate of 70% at month 3, a maximum sample size of 124 evaluable subjects is required for 90% power and preserving a 2.5% (one-sided) type I error rate. This study is designed as a group-sequential trial with 2 interim analyses and a final analysis. The stopping boundaries are derived using the Triangular

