This Clinical Investigational Plan (CIP), informed consent forms (ICF), recruitment materials, and all participant materials will be submitted to the Institutional Review Board (IRB) for review and approval. Approval of the CIP and the ICF must be obtained before any subject is enrolled. Any amendment to the CIP will require review and approval by the IRB before the changes are implemented to the study. In addition, all changes to the ICF will be IRB-approved and a determination will be made regarding whether a new consent needs to be obtained from subjects who previously provided consent.

INVESTIGATOR SIGNATURE PAGE

Investigator Name

Title

Site Name

Site Number

Date

I have read the protocol and agree that it contains all necessary details for carrying out this study. I will conduct the study as outlined therein.

I agree to keep records on all subject information (e.g., source documents and informed consent forms), device shipments and return forms, and all other information collected during the study, in accordance with local and national regulations.

Investigator Signature

SYNOPSIS

Study Title	Latera RCT – Latera [®] Absorbable Nasal Implant vs. Sham Control for Lateral Nasal Valve Collapse		
Spirox Protocol Number	CP04		
Investigational Device	Spirox Latera Absorbable Nasal Implant		
ClinicalTrials.gov Identifier	NCT 03400787		
Sponsor	Spirox, Inc. [name]		
Study Purpose	To evaluate the Latera Absorbable Nasal Implant (Latera Implant) Implant versus Sham Control in subjects with nasal valve collapse due to or primarily due to insufficient cartilaginous support of the lateral nasal wall		
Objective	The primary objective of the LATERA RCT is to demonstrate the superiority of the Latera Implant to improve nasal breathing, compared with a Sham Control treatment.		
Phase of Study	Post-market		
Study Design	Randomized (1:1), sham-controlled, single-blind, multicenter pos market trial using an adaptive trial design		
Investigational Sites	Up to 15 investigational sites in the United States, in office-based locations with investigators experienced in standard nasal interventions for airway obstructions and the use of the Latera Implant		
Study Population	The Adaptive Design allows for enrollment of up to 150 subjects with nasal airway obstruction due to or primarily due to nasal valve collapse.		

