## STATISTICAL ANALYSIS PLAN

The treatment  $(p_T)$  and control  $(p_C)$  will be compared using a 1-sided test for superiority of the following hypothesis:

H0:  $p_T \le p_C$  versus HA:  $p_T > p_C$ 

Where p is the proportion of subjects with a positive response on the primary endpoint assessment. Successful rejection of the null hypothesis will be taken as evidence the device provides reasonable assurance of effectiveness.

A 1-sided binomial test of proportions will be used to compare treatment groups.

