### STATISTICAL ANALYSIS PLAN

moderately aggressive for both effectiveness and futility to reduce the number of subjects enrolled if clear evidence of effectiveness or futility becomes apparent during the trial. When the design assumptions are correct (40% versus 70%), the chance that the trial will stop for effectiveness at the second interim analysis is about 1 in 3. However, if the Latera rate is 85% as seen in the single arm studies, the chance of stopping for effectiveness at the second interim analysis is better than 8 in 10. While all evaluable subjects enrolled at the time of the interim analysis would be followed through 3 months and included in the primary endpoint, an early termination at the second interim analysis could save 20-30% of the total sample size, depending on the enrollment rate.

Interim analyses will be carried out by an independent statistician and reviewed by the independent DMC. The interim analyses will use an alternative to the critical ratio test given below and described by Fleiss. The test results will be compared to the triangular group sequential boundaries. Additional operational details will be found in the DMC Charter.

$$z' = \frac{|p_2 - p_1| - \frac{1}{2}(1/n_{1.} + 1/n_{2.})}{\sqrt{\frac{p_1 q_1}{n_{1.}} + \frac{p_2 q_2}{n_{2.}}}}.$$

			ndaries value)	Cumulative Error Spending		
Analysis	Evaluable (n)	Futility	Efficacy	Type II	Type I	
Interim 1	22	0.7921	0.0005	0.0106	0.0005	
Interim 2	60	0.2139	0.0090	0.0548	0.0093	
Final	124	0.0194	0.0194	0.1000	0.0250	

Table 1. Group Sequential Trial Design – Boundary Information

<sup>3 Fleiss JL, B Levin, MC Paik. Statistical Methods for Rates and Proportions, 3rd Ed. John Wiley & Sons, 2003, (Ch. 3, p 61).

ST 800-A

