### STATISTICAL ANALYSIS PLAN

SAS Code for Nonbinding Beta Boundary

```
proc seqdesign altref=0.3 errspend BOUNDARYSCALE=pvalue;
onesidederrorspending: design nstages=3 info=cum(3.6 8 20)/*3/20,
10/20=1/2, 1*/
method(alpha)=tri(tau=.65)
method(beta)=tri(tau=.65)
alt=upper stop=both (betaboundary=nonbinding)
alpha=0.025 beta=0.10;
samplesize model = twosamplefreq (nullprop=0.4 test=prop);
ods output Boundary=Bnd_Prop_pt5 ;
run;
```

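### The stated 90% power belongs to a test without continuity correction; with the continuity-corrected statistic set for the interims, exact power is about 84–86%

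*SAP*

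**What the plan says.** SAP 2.4 gives the design target. It takes 40% responders on sham and 70% on Latera, and from these concludes that "a maximum sample size of 124 evaluable subjects is required for 90% power and preserving a 2.5% (one-sided) type I error rate". The sizing code in SAP 5.4.4 contains "samplesize model = twosamplefreq (nullprop=0.4 test=prop", with no continuity correction. The Protocol synopsis gives the allocation: "Randomized (1:1), sham-controlled, single-blind, multicenter".

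For the looks themselves, SAP 5.4.4 states: "The interim analyses will use an alternative to the critical ratio test given below and described by Fleiss". The printed z' takes the absolute difference in proportions, subtracts ½(1/n₁ + 1/n₂), and divides by the unpooled standard error. The result is to be compared with the triangular boundaries in the table there, which give looks at 22, 60 and 124 evaluable subjects. Cumulative Type II error in that table is 0.0106, 0.0548 and 0.1000.

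For the primary analysis, SAP 5.2 says only: "A 1-sided binomial test of proportions will be used to compare treatment groups". It gives no formula. SAP 2.4 and 5.4.4 call both boundaries non-binding.

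**The concern.** The boundaries and the sample size were derived for one statistic, and a different one is to be held against them at the interims. The correction is 1/11 = 0.091 at interim 1 and 1/30 = 0.033 at interim 2, against a planned difference of 0.30. Neither the sample size nor the Type II column allows for it.

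The Data Monitoring Committee would be reading a futility boundary whose stated risk of stopping a device that works as planned is not the risk it carries. The sponsor would be relying on 90% power that the specified procedure does not deliver.

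There is also a question of direction. The hypothesis is one-sided, but z' is printed with an absolute value, so a sign convention has to be added before a p-value such as 0.7921 can be applied. The SAP does not supply one, and the choice affects the result.

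**Working it through.** **Inputs.** Sham 40%, Latera 70%, one-sided alpha 0.025, power 90% (SAP 2.4). Allocation 1:1 (Protocol synopsis), so 11, 30 and 62 per arm at the table's 22, 60 and 124. Futility p-values 0.7921, 0.2139, 0.0194; efficacy p-values 0.0005, 0.0090, 0.0194 (SAP 5.4.4). As z-values these are −0.814, 0.793, 2.066 and 3.291, 2.366, 2.066. The table's sample sizes are used because its error columns reproduce with them. The information levels in the SAS code (3.6, 8, 20) do not match the table; with the printed boundaries they would need about 133 subjects.

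**1. Reproduce the plan's figure.** Normal theory, no correction, variance 0.4×0.6 + 0.7×0.3 = 0.45, futility obeyed. Ninety per cent power needs a drift of 3.5128, so n per arm = 3.5128² × 0.45 / 0.30² = 61.7, a total of 123.4, rounded up to 124. Power at 124 is 90.1%. Cumulative Type II is 0.0109/0.0552/0.1000 and cumulative Type I, futility ignored, is 0.0005/0.0093/0.0251. The table agrees within rounding, so 124 and 90% belong to the uncorrected statistic with futility stops counted.

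**2. What the correction does at each look.** On the difference scale, with the planned standard error:

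- Interim 2: SE = √(0.45/30) = 0.1225. The futility threshold moves from 0.793×0.1225 = 0.097 to 0.097 + 0.033 = 0.130. The efficacy threshold moves from 2.366×0.1225 = 0.290 to 0.323.
- Interim 1: SE = √(0.45/11) = 0.202. The futility threshold is −0.814×0.202 = −0.165 uncorrected. It becomes −0.165 − 0.091 = −0.256 if the correction shrinks the difference toward zero (futility harder to reach), or −0.165 + 0.091 = −0.074 if it is always subtracted (futility easier to reach).

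**3. Exact power.** Both binomials were enumerated over per-arm increments of 11, 19 and 32, at 40% v 70% with the tabled boundaries. 'False futility' is a futility stop by interim 2 when those rates are true. The column 'Power, futility ignored' lets the trial continue past the futility boundary.

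| Statistic | Power, futility obeyed | False futility at interim 1 | False futility by interim 2 | Power, futility ignored |
|---|---|---|---|---|
| No correction, unpooled, all looks | 88.2% | 1.7% | 7.1% | 91.9% |
| No correction, pooled, all looks | 87.7% | 1.7% | 7.1% | 91.4% |
| z' at interims, shrink; uncorrected final (unpooled / pooled) | 86.0% / 85.9% | 0.55% | 9.8% | 91.6% / 91.4% |
| z' at interims, always subtract; uncorrected final (unpooled / pooled) | 84.1% / 83.9% | 4.6% | 12.0% | 91.6% / 91.4% |
| z' at all looks (shrink / subtract) | 84.0% / 82.2% | 0.55% / 4.6% | 9.8% / 12.0% | 88.6% |

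**4. Split the shortfall.** From 90.1% to 88.2% (or 87.7%) is about 2 points, due to discreteness. From 88.2% to 86.0% is 2.2 points and to 84.1% is 4.1 points, due to the correction at the interims. With a pooled final test, compared with pooled z throughout, the falls are 87.7 − 85.9 = 1.8 and 87.7 − 83.9 = 3.8 points.

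**5. Sensitivity.** SAP 2.4 puts interim 1 at about 20 subjects, not 22. With 10 per arm there, the interim-only range is 83.5–85.9%.

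**The case against.** The case for leaving z' alone has substance.

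- **The boundaries are non-binding.** If the committee carries on past the futility boundary, power is 91.4–91.6%. This stands, and it means that the loss comes through futility. But the stated 90% itself counts futility stops, since the Type II column accumulates them, so obeying them is the like-for-like comparison.
- **70% is described as conservative.** At the 85% seen in the single-arm studies, power is 99.3–99.8% under every version of z'. This stands as reassurance about the likely outcome. It does not make the stated power at 70% correct.
- **A correction at 11 per arm is a defensible choice.** True. Used at every look, z' keeps exact type I error to about 0.019. The fault is that the sizing and the Type II column do not reflect the choice.

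Some stronger readings are tempting but not supported. A reader might infer that power is 82–84%; that needs z' at the final look too, and the SAP assigns z' to the interims only and gives no formula for the final. A reader might infer that false futility doubles; 9.8–12.0% against 5.48% sets an exact figure against a normal-theory one, and the exact uncorrected figure is already 7.1%. Nor is futility easier to reach at both looks: with shrinkage toward zero, false futility at interim 1 falls from 1.7% to 0.55%, and the increase arises at interim 2 only. Efficacy stopping at interim 2 under z' is 46.0 − 7.05 = 39%, no worse than the one in three or so that the SAP quotes.

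**Conclusion.** The plan is wrong as written, to a moderate degree, and should be corrected. On the specified plan (z' at the interims, an uncorrected final test), exact power at 40% v 70% and 124 evaluable is about 86% with shrinkage toward zero, which is the natural reading of the printed formula, or about 84% if the correction is always subtracted. The chance of missing the planned effect is therefore about 14–16%, not 10%. The correction accounts for about 2–4 points of this; the other 2 or so are discreteness, which an uncorrected test would also incur.

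This rests on equal arms of 11, 30 and 62, the tabled boundaries, futility stops obeyed, and a final test without correction. The last is an assumption, because SAP 5.2 leaves the final statistic undefined. The finding concerns the accuracy of the stated power and Type II error. It does not show that the trial is materially underpowered at the response rates seen earlier, nor that it needs more patients.

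**What to change.** Before the first unblinded look, amend SAP 5.2 and 5.4.4 to name one signed statistic, Latera minus sham, for both interims and the final. One suitable choice is the pooled-variance z without continuity correction. Keep the tabled boundaries. Restate exact power as about 88% at 124 evaluable, and put the Type II column on the same basis: 0.0174, 0.0706 and 1 − 0.8770 = 0.1230.

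Disclose the price: exact type I error for pooled z peaks at about 0.0255 (null rate about 0.32) when futility is ignored, slightly above the 2.5% that SAP 2.4 promises. The unpooled uncorrected z is worse, at about 0.031.

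If z' is kept at the interims, state its sign convention and the formula for the final test, restate power as about 84–86%, and correct the Type II column. With an unpooled uncorrected final it becomes 0.0055/0.0981/0.1403 (shrink) or 0.0464/0.1201/0.1595 (always subtract).

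The cost is SAP wording and restated figures, with no extra patients. Only if the sponsor insists on 90% by exact calculation does the number rise: to about 132 evaluable without correction (unpooled z), or about 144–148 with z' at the interims.

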# STATISTICAL ANALYSIS PLAN

Method, which is a special case of Unified Family (Power) boundaries. A shape parameter of 0.65 will be used, and both boundaries will be non-binding.

Interim analyses will occur when approximately 20 and 60 total subjects have been enrolled and have had their 3-month assessment. The Latera response rate has been observed at approximately 85% in single-arm trials and is likely to be slightly lower in a single blind setting. Thus, 70% is likely a conservative estimate. The placebo response rate observed in pain trials is approximately 30%, and may be even higher in a procedural setting, so 40% was selected for the control response rate used in the study design calculations.

Assuming up to a 10% drop out rate and a 10% potential retrieval rate, the sample size is adjusted to enroll up to 150 subjects to assure adequate sample size with 3 months follow up.

